The base-model variance-covariance structure for the repeated measures data will be unstructured (UN). An autoregressive variance-covariance structure of order 1 [AR(1)] will be tested against the UN variance-covariance structure using likelihood ratio tests. An overall estimate of treatment effect as well as treatment differences will be provided along with the respective 95% confidence intervals (CIs). By-week estimates will be provided as well. All tests of statistical significance will be at two-sided, 0.05 level of significance. As the MMRM analysis assumes that data are missing at random, sensitivity analyses will be performed to assess affects from departure of this assumption.

The primary analyses will be conducted on the ITT population. Secondary analyses of the primary endpoint will be conducted on the PP population. Subgroup analyses of the primary endpoint will be conducted for each level of both stratification factors and for subjects showing at least 2 positive results from the stool or urine gluten tests post baseline, as well as those with 0 or 1 positive tests.

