8.6.1.3 Sensitivity Analyses for Primary Model to evaluate missing data imputation methods

The primary model is a linear mixed model assuming data missing at random (MAR). Sensitivity analyses are done to assess the robustness of the primary efficacy analysis results with respect to different methods of handling missing values, under missing not at random (MNAR) assumption.

For the analysis of the primary efficacy endpoint, missing data will be imputed at the week level using Multiple Imputation (MI) after applying the visit windowing strategy for the CeD PRO weekly scores.

The MI will be carried out following 3 steps:

Step 1. Generation of imputed datasets

The PROC MI procedure of the SAS system with MCMC statement will first be used impute intermittent missingness by treatment group in order to generate 100 sets of data with monotone missingness. Subsequently, PROC MI will be used with MNAR statement indicating the neighboring-case missing values (NCMV) method (Molenberghs and Kenward, 2007) in order to impute the monotone missing values to obtain complete data sets. The imputation model will include treatment group, continuous baseline CeD PRO Abdominal Symptoms domain score, VH:CD at baseline, and CeD PRO Abdominal Symptoms weekly domain score at previous time points as covariates.

Step 2. Model-based analysis using each imputed dataset

Each of the 100 imputed datasets will be analyzed using the primary model specified in Section 8.6.1.2.

Step 3. Pooling the results from each model-based analysis

The results from the analysis of each imputed dataset will be combined using Rubin's rule (Rubin, 1987) by implementing the PROC MIANALYZE procedure of the SAS system.

8.6.1.4 Sensitivity Analyses of Primary Model to Evaluate Effect of Intercurrent Events If evaluation of intercurrent events (Section 8.6.1.1) indicates need for analysis of the primary endpoint in the presence of intercurrent events, the primary analysis will be repeated separately in the mITT analysis set addressing each of the following adjustments, after visit windowing is applied for the CeD PRO weekly data:

Prohibited Medication: Data collected prior to first use of prohibited medication will be used as observed. Time points after first use of prohibited medication will first be set to missing. The MI procedure in Section 8.6.1.3 will then be applied.

Presence of Gluten:

For subjects who do not experience presence of gluten per Section 8.6.1.1, all observed data will be used.

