11.4 SAS Codes

Primary model:

```
proc glimmix data = data;
  class USUBJID TRT(ref = 'Placebo') Week(ref = FIRST);
  model CHANGE = TRT WEEK TRT*WEEK BASEABD BASEVHCD/ solution;
  random _residual_ / subject = USUBJID type = UN;

lsmeans TRT TRT*WEEK /diff cl alpha=0.05;
  ods output LSMeans = LSMeans2;
Ods output diffs = diffs1;
run;
```

Note that the value of type will be changed according to which covariance structure is being fitted (UN).

Multiple Imputation

Step 0. Determine missing patterns in the data

```
proc mi data=data nimpute = 0;
var BASE week2-week24;
ods select misspattern;
run;
```

Step 1. Generation of imputed datasets:

```
Proc mi data = data seed=44853 nimpute=100 out=new data;
 By TRT;
 MCMC impute = MONOTONE;
 var BASE week2-week24;
 run;
 %macro miseq(in=,imputed=,seed=,missing=,out=);
 proc mi data=&in. seed=14823 nimpute=1 out=&out.;
 class TRT;
 by Imputation;
 monotone reg ( &missing. = BASE &imputed. TRT vhcd/details);
 mnar model ( &imputed. &missing. / modelobs= NCMV);
 var BASE TRT vhcd &imputed. &missing.;
run;
 %mend;
%miseq(in=new data, imputed =, seed = 1261, missing = week2, out =
 new data1);
 %miseq(in=new data1, imputed = (Base, week2), seed = 44853, missing =
 week4, out = new data2)
 Etc. .
 Continue until week 24.
```

Imputation using placebo subjects at the same visit (used for imputation of intercurrent events (presence of gluten))

```
proc mi data=new_data seed=14823 nimpute=1 out=outex15;
class flag;
by _Imputation_;
monotone reg (/details);
mnar model( week2-week24 / modelobs= (flag = '1'));
var BASE week2-week24;
run;

/*flag = 1 is for those placebo subjects which did not experience any
presence of gluten*/
```

Step 2. Model-based analysis using each imputed dataset

```
proc glimmix data=new_data2;
    class USUBJID TRT(ref='Placebo') WEEK(ref=FIRST);
    model CHANGE = TRT WEEK TRT*WEEK BASEABD BASEVHCD/ solution;
    by _imputation_;
    random _residual_ / subject=USUBJID type=UN;
    lsmeans TRT TRT* WEEK / diff cl alpha=0.05 cl;
        ods output LSMeans=LSMeans2;
    ods output diffs=diffs1;
run;
```

Step 3. Pooling the results from each model-based analysis

```
proc mianalyze data = lsmeans2;
   by TRT Week;
 modeleffects estimate;
  stderr stderr;
   ods output ParameterEstimates=milsmean;
run:
data diff2;
   set diffs1;
   comparison = TRT||' vs '||left( TRT);
   where Week = 'Placebo' and Week = Week;
run;
proc mianalyze data = diff2;
 by comparison Week;
  modeleffects estimate;

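### The only unconditional missing-data sensitivity analysis is labelled MNAR, but the printed macro is a MAR regression, and NCMV as worded has too few donors to be fitted at most of Weeks 2-22

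*SAP*

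**What the plan says.** Protocol 9.4.2 notes that the MMRM assumes data missing at random and commits that "sensitivity analyses will be performed to assess affects from departure of this assumption".

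SAP 8.6.1.3 is where this is delivered. Intermittent gaps are first filled by MCMC within arm, giving 100 monotone data sets. Then "PROC MI will be used with MNAR statement indicating the neighboring-case missing values (NCMV) method" for the remaining missing weeks. The imputation model contains treatment, baseline score, baseline VH:CD and "CeD PRO Abdominal Symptoms weekly domain score at previous time points as covariates". Each data set is analysed with the 8.6.1.2 model and pooled by Rubin's rules.

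Appendix 11.4 implements the NCMV step with a macro called once per week. Its working lines are "monotone reg ( &missing. = BASE &imputed. TRT vhcd/details", "mnar model ( &imputed. &missing. / modelobs= NCMV" and "var BASE TRT vhcd &imputed. &missing".

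No other section tests missing post-baseline data unconditionally:

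- SAP 8.6.1.4 runs only if review of intercurrent events calls for it. Its placebo-donor step is for gluten-positive visits, and its prohibited-medication analysis reuses the 8.6.1.3 procedure.
- SAP 8.6.1.5 concerns the baseline definition.

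SAP 8.2 allows the appendix code to be changed without an amendment.

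**The concern.** NCMV imputes a missing week k from subjects whose last observed week is k (completers, for Week 24). That has two consequences.

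- The software must see week k+1 to know who those subjects are. The printed macro never shows it a later week.
- The donors are one dropout pattern at a time, which in a trial of about 220 subjects is a handful of people. They must support a regression that gains a parameter at every visit.

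If the code is run with its printed variable list, a second MAR analysis will sit beside the primary MAR analysis. Their agreement would be reported as robustness under MNAR. If the text is followed instead, most weeks cannot be fitted, and a substitute would have to be chosen at the time of analysis with no rule in the SAP. Dose selection is to rest on all the evidence together, so the label on this analysis carries weight.

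**Working it through.** **Inputs.** From SAP 7: about 220 randomised, 55 per arm, 50 evaluable per arm, a difference of 0.40, 80% power, two-sided 0.05. From SAP 8.6.1.2: 12 analysis visits (Weeks 2, 4, ..., 24). The covariates are those of SAP 8.6.1.3.

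*Assumptions:* the documents give no dropout rate. Reading 50 of 55 as loss gives 1 - 50/55 = 9.1%, so 9% to 40% is shown. The planned SD is redacted, so the stated power cannot be reproduced. Solving backwards, SD = 0.40/(2.80 x sqrt(2/50)) = 0.40/0.56 = 0.714, and the standard error of a contrast is 0.714 x sqrt(2/50) = 0.14.

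**Step 1: what the macro does.** When week k is imputed, earlier weeks are already filled and week k is the last variable listed. The only patterns visible are week k observed and week k missing. The donors are therefore everyone observed at week k, with treatment as a covariate, which is sequential MAR regression. This follows from the variable list and needs no dropout assumption. A Python re-implementation (SAS was not run) matched an explicit MAR regression in 200 of 200 simulated trials. In a very large sample with 30% MNAR dropout, the imputed mean was 3.845 for both macro and MAR, 4.006 for true NCMV, and the truth was 4.063.

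**Step 2: parameters in the worded NCMV.** Week 2: intercept 1 + baseline 1 + treatment 3 + VH:CD 1 = 6. Each earlier week adds 1, so Week 22 has 6 + 10 = 16.

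**Step 3: donors.** Dropouts are spread evenly over 12 intervals, arms pooled as the SAP does, 20,000 multinomial draws. A week counts as fittable if donors exceed parameters.

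| Dropout | 9% | 20% | 30% | 40% |
|---|---|---|---|---|
| Dropouts of 220 | 20 | 44 | 66 | 88 |
| Donors per week (dropouts/12) | 1.7 | 3.7 | 5.5 | 7.3 |
| Weeks of 11 fittable | 0.00 | 0.11 | 0.66 | 1.8 |
| Same, front-loaded dropout | 0.02 | 0.70 | 2.0 | 3.2 |
| Weeks of 11 with no donor | 1.9 | 0.2 | 0.04 | 0.01 |

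Fitting all 11 weeks needs 7 + 8 + ... + 17 = 132 dropouts, or 60% of 220, exactly placed. At 9%, 10.8 of the 11 weeks still need imputation on average.

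**Step 4: numerical effect.** Simulation of 250 trials per rate and mechanism, 4 x 55 subjects, correlation 0.5 + 0.5 x 0.6^lag, dropout only with no intermittent gaps. The effect is -0.40 until dropout and 0 after. Mechanism A: dropout unrelated to outcome. Mechanism B: dropout more likely with a worse unseen score.

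| Dropout | 9% | 20% | 30% | 40% |
|---|---|---|---|---|
| A: full data | -0.389 | -0.357 | -0.334 | -0.291 |
| A: MMRM | -0.409 | -0.403 | -0.398 | -0.377 |
| A: macro | -0.408 | -0.403 | -0.398 | -0.377 |
| A: MMRM overstatement | 0.02 | 0.05 | 0.06 | 0.09 |
| B: MMRM overstatement | 0.01 | 0.03 | 0.04 | 0.06 |
| A: macro minus MMRM, 95th percentile of absolute value | 0.006 | 0.008 | 0.010 | 0.013 |

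The largest single-trial difference between macro and MMRM under A was 0.024. Under A the macro reproduces the MMRM's overstatement and gives no warning of it; the same held for the mean estimates under B.

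**The case against.** **The code is not binding.** SAP 8.2 lets it change, and the block is visibly a sketch. One call passes "imputed = (Base, week2), seed = 44853, missing", which is not a plain variable list and repeats the baseline. The line "proc mi data=&in. seed=14823 nimpute=1 out=&out" ignores the seed argument. This stands in part: the macro finding concerns the code as printed, with its arguments tidied. But restoring later weeks to the variable list brings back true NCMV, and with it the donor shortage in the binding text.

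**NCMV is a recognised MNAR method.** This stands. A reader might infer that it is MAR in disguise or cannot be rescued, and neither follows. In large samples it departs from MAR under mechanism B (-0.405 against -0.392). Pooling all later dropouts and holding the regression to 6 parameters makes 7.5/9.6/10.2/10.6 of 11 weeks fittable at 9/20/30/40%. The SAP states no such rule. NCMV also does not probe loss of effect after dropout (mechanism A at 9%: NCMV -0.397, MAR -0.398, full data -0.378), because its donors are still in the study at that visit. Protocol 9.4.2 does not ask for that particular departure, so this is a reason to add an analysis and not an error in the plan.

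**There are donors.** This stands. A reader might take the shortage to mean none, but with arms pooled only 1.9 of 11 weeks have no donor at 9%. The shortage is relative to the stated model. Week 24 draws on completers and is unaffected.

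**Materiality.** The effect is small at the one rate that can be inferred from the documents. SAP 8.2.4 encourages visits after treatment stops, which would shrink it further, and SAP 7 declares the results exploratory. This stands and limits the weight of the point.

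**Conclusion.** The point holds. As printed, the macro is MAR. As worded, NCMV cannot be fitted at most of Weeks 2-22 at any dropout rate from 9% to 40%. The prohibited-medication analysis in SAP 8.6.1.4 would inherit the same problem.

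The first conclusion rests only on the printed variable list. The second rests on an assumed dropout rate and timing, but front-loaded dropout did not change it. How SAS behaves with too few donors is not in the documents and was not relied on.

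The numerical figures are softer. They assume the SD and the correlation, and omit the intermittent gaps that the four-diary-days rule makes likely. A reader might infer that macro and MMRM must agree within 0.01 in every trial; the simulation supports about that as typical, with 0.024 the largest seen. A reader might also infer that the primary result is unsafe. The documents do not support that: at about 9% dropout the overstatement is 0.01-0.02 points, against a standard error of about 0.14, even if all effect is lost after dropout. It would matter more with higher dropout or a confidence limit close to 0. The main harm is the wrong label.

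**What to change.** Before unblinding, reconcile SAP 8.6.1.3 with Appendix 11.4 and name one estimable MNAR analysis. Suggested text:

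> After MCMC imputation of intermittent gaps, monotone missing weeks are imputed under MAR by sequential regression within arm. When imputation is complete, shifts from 0 upward over a prespecified grid are added to the imputed monotone-missing weekly scores in the active arms only. The overall contrast with placebo and its 95% CI are reported for every dose at every shift, using the 8.6.1.2 model and Rubin's rules.

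The sponsor should justify the grid range. In the simulation at 9% dropout (mechanism A), among doses whose CI excluded 0 under MAR, the median shift needed to lose that was 2.7 points. Reporting every shift is therefore more useful than a tipping point alone.

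Copy-reference imputation from placebo may be added as a named supplement. In the simulation it moved about 40% of the way from the MMRM to the full-data value under mechanism A. The placebo-donor block in Appendix 11.4 can be adapted for it.

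If NCMV is kept, put all weeks in one variable list. State a rule that pools later dropouts and limits the covariates (for example, at most 6 parameters), and give a fallback for weeks that still cannot be fitted. Correct the macro's arguments and seed. State which procedure the prohibited-medication analysis in 8.6.1.4 then uses.

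**Cost.** SAP text and one program, with no new data. The by-arm regressions are estimable: at Week 24 they have 14 parameters (intercept, baseline, VH:CD, 11 earlier weeks) against about 50 observed per arm at 9% dropout and 33 at 40%. The downside is some programming and possibly slightly less favourable sensitivity results.

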8.6.1.5 Sensitivity Analysis of Primary Model to Evaluate Alternate Baseline Definition

In some instances, randomized patients who needed to be rescheduled for their Visit 3 (e.g., first dose of double-blind treatment) experienced delays between the end of their run-in period and the first dose of double-blind treatment. In this regard, a sensitivity analysis will be conducted for the primary model (Section 8.6.1.2) in the mITT analysis set to use the following baseline definition for the CeD PRO Abdominal symptoms domain:

Average of scores from 7 days prior to the first dose of double-blind treatment.

In some instances, subjects were not compliant with completing the CED PRO questionnaire daily in the week prior to randomization. In this regard, a sensitivity analysis will be conducted for the primary model (Section 8.6.1.2) in the mITT analysis set to use the following baseline definition for the CeD PRO Abdominal symptoms domain:

 Alternative baseline will be defined as the 'Average of scores from 10 days prior to randomization (e.g., last 10 days of placebo run-in)'.

8.6.1.6 Subgroup Analyses of Primary Model

Subgroup analyses will be conducted in the mITT analysis set to explore the consistency of treatment effects in the following subgroups:

- VH:CD ratio (<2, >=2)
- Baseline CeD PRO Abdominal Symptoms domain score (<3, >=3)

For each subgroup, models similar to the primary model will be fit separately for each level of the subgroup.

8.6.2 Secondary Efficacy Variable(s)

Secondary efficacy variables of the study are:

- Absolute change from baseline through Week 24 in the Diarrhea and Loose Stool domain of the CeD PRO.
- Absolute change from baseline through Week 24 in gastrointestinal (GI) symptoms as assessed by the Total GI score (comprising the Abdominal Symptoms domain, the Diarrhea and Loose Stool domain, and the Nausea item) of the CeD PRO.
- Absolute change from baseline to Week 24 in small intestinal mucosal inflammation, as measured by intraepithelial lymphocyte (IEL) density using immunohistochemistry (IHC).

8.6.2.1 CeD PRO Diarrhea and Loose Stool Domain

The same type of model as for the primary endpoint will be fitted to the secondary CeD PRO endpoint for the change from baseline in Diarrhea and Loose Stool domain; i.e. including treatment, week, and week by treatment as fixed effects, the continuous baseline Abdominal Symptoms domain score and VH:CD ratio as covariates, and subject as a random effect.

These analyses will be done on the mITT analysis set and repeated on the PP analysis set.

8.6.2.2 Total GI Score

The same type of model as for the primary endpoint will be fitted to the secondary CeD PRO endpoint for the change from baseline in Total GI score (comprising the Abdominal Symptoms domain, the Diarrhea and Loose stool domain, and the Nausea item); i.e. including treatment, week, and week by treatment as fixed effects, the continuous baseline Abdominal Symptoms domain score and VH:CD ratio as covariates, and subject as a random effect.

These analyses will be repeated for the Total GI Score (excluding Nausea).

These analyses will be done on the mITT analysis set and repeated on the PP analysis set.

8.6.2.3 IEL Density

The absolute change from baseline to Week 24 in small intestinal mucosal inflammation, as measured by IEL density (cells/100 epithelial cells) using IHC will be analyzed using analysis of covariance (ANCOVA), where the continuous baseline Abdominal Symptoms domain score and VH:CD ratio are included as covariates and treatment as fixed effect.

The following model will be fitted:

 $Y_{ij} = \mu + \alpha_j + \beta_1 \cdot baseline \ Abdominal \ Symptoms \ score_{ij} + \beta_2 \cdot baseline \ VH: CD \ ratio_{ij} + \varepsilon_{ij},$ where

 Y_{ij} is the change from baseline to week 24 in small intestinal mucosal inflammation for subject i ($i = 1, ..., n_j$) from treatment group j (j = 1, 2, 3, 4),

 μ is the overall mean change from baseline,

 α_j is the fixed effect due to treatment j,

 β_1 is the parameter estimate for the baseline Abdominal Symptoms score,

 β_2 is the parameter estimate for the baseline VH:CD ratio,

 ε_{ij} is the random error term for subject i from treatment group j.

The modelling results (ANOVA table, parameter estimates, estimated treatment effect, marginal (i.e. least squares) means estimates and results of the check of assumptions, i.e. the check of common variance assumption) will be tabulated and 95% confidence intervals added, where appropriate.

The common variance assumption check is done using Levene's test.

This analysis will be done on the mITT analysis set and repeated on the PP analysis set.

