8.2.7. Esophagogastroduodenoscopy (EGD) and Histological Assessments

At each time point specified in the SoA (Section 1.3), at a minimum, 6 biopsies or specimens of small-bowel tissue will be taken from the second part of the duodenum distal to the ampulla (duodenum D2) by EGD and endoscopic forceps biopsy. Ulcerative lesions should be avoided for all biopsies. The biopsies should be opaque and not translucent or stringy. Poor specimens should be replaced. The location and macroscopic appearance of the tissue will be noted in the source documents. The potential presence of any observable lesion such as ulcerative jejunitis will also be captured. When necessary, samples will be re-oriented and sectioned again until they are of good quality. The procedures will be described in a Study or Laboratory Manual or a similar document. The biopsies or specimens will be prioritized as follows:

1. All 6 specimens will be fixed in PAXgene at the site (see Central Laboratory Manual) and shipped to the Central Pathologist.
2. The Central Pathologist, blinded to treatment assignment, will assess villus height (VH, in micrometers) and crypt depth (CD, in micrometers) and their ratio, VH:CD, using 4 specimens. Further, the Marsh-Oberhuber histology score will be given (M0, M1, M2, M3a, M3b, or M3c) and the density of CD3-positive IELs (cells/100 epithelial cells) will be assessed. Histology analysis will be performed following standard operating procedures for fixed biopsy specimen orientation, paraffin embedding, cutting, staining, and scanning for whole slide virtual microscopy. Standard operating procedures will also be followed for biopsy morphometry readings using validated methods (Taavela 2013). If it is not feasible to measure at least 3 villus-crypt units for a subject's given biopsies, even after re-cutting, the results will be considered not evaluable.
3. Two specimens will be placed in a messenger ribonucleic acid (mRNA) preservative for future mRNA analysis of inflammatory pathways (e.g., expression analysis of IL-15-related pathways to potentially identify predictive biomarkers of response to PRV-015).

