5 RANDOMIZATION

All subjects will be centrally assigned to randomized study drug (placebo or 1 of 3 doses of PRV-015) after the single-blind, placebo run-in period using an Interactive Voice/Web Response System (IVRS/IWRS). Before the study is initiated, the telephone number and call-in directions for the IVRS and/or the log-in information and directions for the IWRS will be provided to each site.

Subjects will be randomly assigned in a 1:1:1:1 ratio, stratified by baseline VH:CD of <2 or ≥ 2 (assessed during the placebo run-in period) and by the CeD PRO Abdominal Symptoms domain score of <3 or ≥ 3 at baseline, using the average of the Abdominal Symptoms domain scores over the last week of the run-in period immediately before randomization.

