7 ESTIMATION OF SAMPLE SIZE

A proposed sample size of approximately 50 evaluable subjects within each treatment group would provide approximately 80% power to detect a 0.40 difference from placebo and any given active treatment group at the two-sided, 0.05 level of significance in the primary endpoint, change through Week 24 in the Abdominal Symptoms domain score in CeD PRO. These calculations are based on the assumption of a within-subject standard deviation (SD), as derived in the CELIM-NRCD-001 trial using the mixed effect modelling for repeated measures (MMRM) analyses. An approximate difference in the overall least squares (LS) means through 16 weeks in the treatment period was observed between the active (300 mg) and placebo groups. The overall estimate through 16 weeks was observed to be for placebo versus for the 300 mg treatment group. Of note, the estimated difference at week 16 was however, the more conservative overall difference of was used in the calculation of sample size. The results and their ranking are exploratory in nature, and the selection of endpoints and dose for confirmatory studies will be based on the totality of evidence. As such, these calculations are not adjusted for multiplicity.

Approximately 220 subjects will be randomized at a ratio of 1:1:1:1 to PRV-015 100 mg, 300 mg, 600 mg, or placebo (approximately 55 subjects per group). Subjects will be stratified by normal or abnormal baseline VH:CD (i.e., <2 or \ge 2) and by the CeD PRO Abdominal Symptoms domain score of <3 or \ge 3 at baseline using the average of the Abdominal Symptoms domain scores over the last week of the single-blind placebo run-in period immediately before

Confidential Page

randomization. The number of subjects with Marsh score 0 or 1 will be capped at approximately 72. Withdrawn subjects will not be replaced.

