8.2.2 Definition of Derived Variables

8.2.2.1 Patient-reported Assessments Captured in eDiary

CeD PRO Domain Scores

The CeD PRO is captured daily in the eDiary after the last meal of the day before the subject goes to bed. It includes 9 items asking participants about the severity of celiac disease symptoms they may experience each day. Participants are asked to rate their symptom severity on an 11-point (0 to 10) scale; from "not experiencing the symptom" to "the worst possible symptom experience". Symptoms include abdominal cramping, abdominal pain, bloating, gas, diarrhea, loose stool, nausea, headache, and tiredness (Figure 2).

[figure not shown]
Analyses will be performed on all individual domain scores and weekly worst symptom domain scores in the GI symptom domains (Abdominal Symptoms and Diarrhea/Loose Stool domains) and Total GI score (Abdominal Symptoms Domain + Diarrhea/Loose Stool Domain + Nausea item). The Total GI score will be assessed with and without inclusion of the Nausea item.

Daily mean domain score is calculated as sum of daily item scores for all items within a domain divided by number of items in the domain.

Weekly domain scores are based on analysis visit windows (defined below) and calculated as the sum of non-missing daily mean domain scores divided by the number of non-missing scores of a given week. A weekly score is calculated if there are at least 4 non-missing daily scores available. Weekly mean total GI score is calculated as the sum of weekly mean Abdominal Symptoms domain score, Diarrhea and Loose Stools domain score, and Nausea item score divided by 3. The weekly mean total GI domain score without the Nausea item, is calculated as the sum of weekly mean Abdominal Symptoms domain score, Diarrhea and Loose Stools domain score divided by 2. If any of the weekly domains are missing, the total score will be calculated as the average over the remainder non-missing weekly domain scores.

Figure 2. Symptom Domains in the Celiac Disease Patient-Reported Outcome Questionnaire

CeD PRO Symptomatic Days

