8.6.2.4 Subgroup analyses for secondary efficacy variables

Subgroup analysis will be done for all three secondary endpoints using the same subgroups as described in Section 8.6.1.6. The subgroup analyses for the secondary endpoints will be done on the mITT analysis set only. The same type of models as used for the secondary endpoints will also be fit separately for each level of the subgroup.

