 stderr stderr;
   ods output parameterestimates=midiff;
run;
Analysis of covariance (ANCOVA)
(IEL Density)
proc glm data = data alpha=0.05 outstat = F tests;
   class TRT(ref='Placebo');
   model CHANGE = TRT BASEABD BASEVHCD/ clparm solution SS1 SS2;
   estimate "PRV-015 100 mg vs Placebo" TRT 1 0 0 -1;
   estimate "PRV-015 300 mg vs Placebo" TRT 0 1 0 -1;
   estimate "PRV-015 600 mg vs Placebo" TRT 0 0 1 -1;
   1smeans TRT /cl stderr alpha=0.05 pdiff = all;
   ods output ParameterEstimates=Par est LSMeanCL=LS meanCL
      LSMeans=LS mean OverallANOVA=ANOVA Estimates=Eff est;
run;
Levene's test
proc glm data = data alpha = 0.05;
 class TRT;
  model CHANGE = TRT / clparm solution SS1 SS2;
   means TRT / hovtest;
   ods output HOVFTest = Levene;
run;
```

Chi-square test:

```
proc freq data = data;
  tables TRT*REDUCBLX / chisq;
  output out=CHiSqData pchi;
```

run;

where REDUCBLX shows if subject had X% reduction from baseline at Week 24.

The Cochran-Mantel-Haenszel test (CMH)

```
proc freq data=data;
  tables BLMED*TRT*RESPONSE / cmh scores=modridit;
  output out=outdata;
run;
```

where BLMED is baseline Marsh-Oberhuber score (M0, M1, M2 vs. M3a, M3b, M3c) score and RESPONSE shows if subjects have worsening scores.

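### The secondary efficacy models leave out each endpoint's own baseline, giving up precision and letting chance baseline imbalance move the estimates

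*SAP*

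**What the plan says.** All three secondary efficacy endpoints are changes from baseline.

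- **Diarrhea and Loose Stool (SAP 8.6.2.1) and Total GI score (8.6.2.2).** Both use a repeated-measures model with "treatment, week, and week by treatment as fixed effects, the continuous baseline Abdominal Symptoms domain score and VH:CD ratio as covariates", plus subject as a random effect.
- **IEL density (8.6.2.3).** This is an ANCOVA in which "the continuous baseline Abdominal Symptoms domain score and VH:CD ratio are included as covariates and treatment as fixed effect". The written equation has the same terms, and so does the code in 11.4: "model CHANGE = TRT BASEABD BASEVHCD/ clparm solution SS1 SS2".
- **Subgroups (8.6.2.4).** "The same type of models as used for the secondary endpoints will also be fit separately for each level of the subgroup".

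The list is that of the primary model (8.6.1.2), where baseline Abdominal Symptoms is the endpoint's own baseline. The two covariates are also the stratification variables (SAP 5), with the symptom score taken "using the average of the Abdominal Symptoms domain scores over the last week of the run-in period immediately before randomization".

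Protocol 9.4.3 says only that the secondary analyses will be comparable to the primary one. The list of changes in SAP 8.10 does not discuss the covariates.

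**The concern.** In the primary model, baseline Abdominal Symptoms does two jobs: it represents a stratification factor and it adjusts for the endpoint's own starting value. Carried unchanged to other endpoints, it keeps only the first job.

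A change score subtracts the whole baseline, which fixes the baseline slope at 1. When the true slope is below 1, subjects who start high tend to fall and subjects who start low tend to rise. Change is then negatively correlated with baseline. Unless baseline is in the model, that variation stays in the residual, and an arm that happens to start worse appears to improve more.

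The present covariates replace the own baseline to different degrees:

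- **IEL density.** VH:CD may carry part of the information. Randomization is not stratified on IEL density.
- **Diarrhea and Loose Stool.** Protocol 5.1 sets a minimum run-in score for Abdominal Symptoms but none for diarrhea, so subjects can enter with little diarrhea and little room to improve.
- **Total GI.** Here the loss is smallest: "Weekly mean total GI score is calculated as the sum of weekly mean Abdominal Symptoms domain score" with the two other components, divided by three (by two without Nausea).

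IEL density is the only histology endpoint among the secondary endpoints. SAP 7 says "the selection of endpoints and dose for confirmatory studies will be based on the totality of evidence", and no test is adjusted for multiplicity. Avoidable noise in these estimates therefore enters the choice of dose and endpoint.

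**Working it through.** **Inputs.** From the documents: about 50 evaluable subjects per arm (SAP 7), two-sided 0.05 (SAP 8.2), 12 analysis visits from Week 2 to Week 24 (SAP 8.2.2.1). The plan gives no power or precision for any secondary endpoint, so there is no stated figure to reproduce.

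Assumed, because the documents give none:

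- r: correlation of the endpoint's own baseline with follow-up.
- R²: share of own-baseline variance explained by the planned covariates.
- Unit SD at every visit, and no further link between the planned covariates and follow-up once the own baseline is known.

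**Single visit (IEL).** Residual variance with own baseline is 1 − r². The planned model adds (1 − r)²(1 − R²). The ratio k of planned to own-baseline variance is 1 + (1 − r)²(1 − R²)/(1 − r²). For an effect with 80% power under the own-baseline model, planned power is Φ[(1.960 + 0.842)/√k − 1.960].

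| r | k at R² = 0 | k at R² = 0.36 | Power |
|---|---|---|---|
| 0.3 | 1 + 0.49/0.91 = 1.54 | 1.35 | 62–68% |
| 0.5 | 1 + 0.25/0.75 = 1.33 | 1.21 | 68–72% |
| 0.7 | 1 + 0.09/0.51 = 1.18 | 1.11 | 73–76% |

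At the extremes this is like analysing 50/1.54 ≈ 32 or 50/1.11 ≈ 45 subjects per arm instead of 50.

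**Average over 12 visits (CeD PRO scores).** With the same correlation r between any two time points, the own-baseline residual variance is (1 + 11r)/12 − r²: 0.2917 at r = 0.5 and 0.235 at r = 0.7. The added term is again (1 − r)²(1 − R²). Assuming equal SDs and a correlation c = 0.5 between components, R² is c² = 0.25 for Diarrhea and Loose Stool, (1 + 2c)/3 = 0.67 for Total GI, and (1 + c)/2 = 0.75 for Total GI without Nausea.

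| Endpoint | k, r = 0.5 | k, r = 0.7 | Power |
|---|---|---|---|
| Diarrhea/Loose Stool | 1 + 0.1875/0.2917 = 1.64 | 1 + 0.0675/0.235 = 1.29 | 59–70% |
| Total GI | 1.29 | 1.13 | 70–75% |
| Total GI without Nausea | 1.21 | 1.10 | 72–76% |

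If the planned covariates carried no information on the own baseline (R² = 0), the ratios would be 1.86 and 1.38.

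**Shift from a chance imbalance.** With 50 per arm, one standard error of a baseline difference is √(2/50) = 0.2 SD. The expected shift is 0.2(1 − r)(1 − R²): 0.04 to 0.14 SD for IEL, 0.05 to 0.08 SD for Diarrhea and Loose Stool, and 0.02 to 0.03 SD for Total GI.

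**Simulation.**

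- Four arms of 50, complete data, ANCOVA on subject means, 4,000 runs per setting. Power of the planned model against the model with own baseline: IEL at r = 0.5, 69% against 79%; Diarrhea and Loose Stool, 59% against 79% (r = 0.5) and 69% against 79% (r = 0.7); Total GI, 68% against 79% and 74% against 79%. Mean bias was within 0.003 SD and type I error 4.5% to 5.6% in both models.
- Two arms of 50, no effect, r = 0.5, 10,000 trials per setting. Among trials with an own-baseline imbalance above 0.3 SD, the planned model was off by 0.20 SD (R² = 0) or 0.15 SD (R² = 0.25), with conditional type I error of 14% or 10%. With own baseline included, the shift was at most 0.012 SD and the error 5% to 7%.

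**The case against.** **There is no validity error.** The change score is unbiased over randomizations, type I error holds, the stratification variables are in the model, and Protocol 9.4.3 promises only comparable analyses. This is correct. The point concerns efficiency and conditional accuracy on secondary endpoints of a trial that calls its results exploratory.

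**The two harms are one.** The extra variance, (1 − r)²(1 − R²), is the variance of the imbalance-driven shift, and the planned intervals already contain it. This stands: the shift is the conditional view of the same loss and should not be counted twice.

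**The figures for the averaged endpoints are favourable to the concern.** They use one correlation both for baseline with follow-up and for follow-up visits with each other. With 0.5 for the former and 0.7 for the latter, the own-baseline residual is (1 + 7.7)/12 − 0.25 = 0.475. The ratios become 1 + 0.1875/0.475 = 1.39 for Diarrhea and Loose Stool and 1 + 0.0833/0.475 = 1.18 for Total GI. At 0.8 throughout, the residual is (1 + 8.8)/12 − 0.64 = 0.1767, and the ratios are 1 + 0.030/0.1767 = 1.17 and 1 + 0.0133/0.1767 = 1.08. This stands as a caveat on size; the direction does not change.

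**The power figures use a chosen benchmark.** They refer to an effect defined to have 80% power with own baseline included. They are not a shortfall against a figure in the plan.

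**The effect in subgroups is not quantified.** Splitting at an Abdominal Symptoms score of 3 restricts that covariate's range and weakens it as a substitute. The VH:CD split does not restrict it, and the upper symptom stratum still spans 3 to 10. The R² = 0 ratios should not be read as subgroup results.

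**The simulations did not fit the planned unstructured repeated-measures model with missing visits.** This is true; they check the formulas, not the exact analysis.

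**Conclusion.** The concern holds. The omission is explicit in the text of all three secondary models and in the IEL equation and code, and nothing elsewhere in either document supplies the missing terms. The cost is precision, together with estimates that move when an arm happens to start worse or better. Average bias and overall type I error are not affected, and neither is the primary analysis.

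Allowing for the alternative correlations above, the variance inflation is roughly 11% to 54% for IEL density, 17% to 64% for Diarrhea and Loose Stool, and 8% to 29% for Total GI with Nausea. A stronger substitute covariate or a higher correlation would make it smaller still. That the omission exists and in which direction it acts are certain; the sizes rest on assumed correlations. The change should be made because it is nearly free, but the analyses would be valid without it.

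**What to change.** Before unblinding, add the endpoint's own baseline to each secondary model and keep baseline Abdominal Symptoms and VH:CD.

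- **8.6.2.3 and 11.4:** add a term β₃ × baseline IEL density to the equation, and a matching variable (for example `BASEIEL`) to the MODEL statement.
- **8.6.2.1:** add the baseline Diarrhea and Loose Stool weekly score.
- **8.6.2.2:** add the baseline Total GI score, with or without Nausea to match the outcome.
- **8.6.2.4:** carry the added term into the subgroup models.
- **8.6.3:** in the exploratory repeated-measures models, add the baseline weekly worst score, or the baseline-month symptomatic days, for the domain analysed. The gain is mainly for domains other than Abdominal Symptoms; its size was not calculated.

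Leave the primary model as it is. SAP 8.2 allows code changes without an amendment, but here the model text must change too.

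The cost is one degree of freedom per model, among about 200 subjects in the full analyses and fewer in subgroups, plus a short edit. The data already exist: Protocol 8.2.7 provides that at each biopsy "the density of CD3-positive IELs (cells/100 epithelial cells) will be assessed", and the CeD PRO baselines come from the daily eDiary. No subject is lost, because a subject without the own baseline has no change score.
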